**Abbreviations List**

VAS: Visual Analog Scale

**Research Summary**

**Study Population –**

80-100 patients to be recruited.

**Inclusion Criteria:**

Adult

Single trigger injection

First time for the digit

No prior surgery on digit

**Exclusion Criteria:**

Current oral steroid use

Rheumatoid arthritis

More than one single digit involved

Previous injection in same digit

Prior surgery on same digit

Other injections in the same clinic on the same day

## OFFICE OF HUMAN RESEARCH PROTECTION

**Study Design** – The two standard of care corticosteroids used for trigger finger treatment are betamethasone and methylprednisolone. Both injections are effective in treating trigger finger and the decision of which to use in treatment is currently a matter of the current practice and physician preference. There is no literature comparing the side effects, specifically flare reactions between these two treatments. Our goal through this randomized trial is to see whether there is a difference between these two corticosteroids in inducing flare reactions and if there are any differences in the peak level of pain and its duration. We will carry out a double-blinded randomized trial enrolling patients into one of the two treatment groups. The volume of the doses of steroid to be given will be standardized to 1 cc of either methylprednisolone (40 mg) or betamethasone (6 mg). We will instruct patients who meet the inclusion criteria to complete a visual analog scale (VAS) of their pain (1-10) prior to the injection, immediately after the injection, five minutes after the injection, and once a day for a minimum of 7 days after the injection. The incidence, intensity, time to peak and time to resolution of the flare reactions (defined as a 2-point increase from pre-injection pain) will be assessed and compared between the two groups. Findings indicating a statistically significant difference in the incidence and/or intensity of the flare reactions would be clinically significant and would be evidence supporting the switch of current standard practice to one corticosteroid over the other. Patients will only receive a single, standard of care, trigger finger injection on the day they present to the clinic. The next 7 days, up to two weeks if needed, of follow-up will only be a single short survey question to determine pain level.

Patients will be identified by the surgeon on the day they present to clinic, and will be recruited and consented by the study personnel. Data will be collected from the patient and stored in the REDCap server. There is not more than minimal risk involved.

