## Section II: Design

### Background & Significance

Corticosteroid injections are effective non-surgical approach to treating trigger finger (stenosing tenosynovitis) with success rates reported as high as 92% after just one injection [1]. Among their side effects is a post-injection flare of increased pain that is attributed to crystal-induced synovitis [2]. Reports of these flares in the literature have been rare. Recent evidence their incidence can be as high as 33% [3]. We feel they are a more common clinical issue than traditionally reported and it would be beneficial to control and reduce their incidence if possible.

Two common corticosteroids used for trigger finger treatment are betamethasone and methylprednisolone [4][5]. Both injections are effective in treating trigger finger and the decision of which to use in treatment is currently a matter of the current practice and physician preference. There is no literature comparing the side effects, specifically flare reactions between these two treatments. Our goal through this randomized trial is to see whether there is a difference between

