## OFFICE OF HUMAN RESEARCH PROTECTION

these two corticosteroids in inducing flare reactions and if there are any differences in the peak level of pain and their duration.

We will carry out a double-blinded randomized trial enrolling patients into one of the two treatment groups. The volume of the doses will be standardized to 1 cc of either methylprednisolone (40 mg) or betamethasone (6 mg). We will instruct patients who meet the inclusion criteria to complete a visual analog scale (VAS) of their pain (1-10) prior to the injection, during the injection and once a day for the following 7 days after the injection. We estimate that we need a minimum of 30 patients in each group to achieve a minimum of 80% power and 0.05 significance. The incidence, intensity, time to peak and time to resolution of the flare reactions (defined as a 2-point increase from pre-injection pain [3]) will be assessed and compared between the two groups. Findings indicating a statistically significant difference in the incidence and/or intensity of the flare reactions would be clinically significant and would be evidence supporting the switch of current practice to one corticosteroid over the other.

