**REFERENCES:** See References section**Objectives**

Two common corticosteroids used for trigger finger treatment are betamethasone and methylprednisolone. Both injections are effective in treating trigger finger and the decision of which to use in treatment is currently a matter of the current practice and physician preference. There is no literature comparing the side effects, specifically flare reactions between these two treatments. Our goal through this randomized trial is to see whether there is a difference between these two corticosteroids in inducing flare reactions and if there are any differences in the peak level of pain and their duration.

Findings indicating a statistically significant difference in the incidence and/or intensity of the flare reactions would be clinically significant and would be evidence supporting the switch of current practice to one corticosteroid over the other.

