### Risk & Benefit

***Risk*** – Risks from participation in this study include typical risks associated with a trigger finger injection: pain at injection site, soreness, etc.

***Benefit*** – The subject will receive no direct benefits. Knowledge gained from this study could help change standard of care procedures for trigger finger injections to best limit flare reactions afterward.

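### The flare definition has no time window, so a 2-point pain rise at the in-clinic readings counts as a flare if the rule is applied as written

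*Combined protocol and SAP*

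**What the plan says.** The Study Design text of the Research Summary names four outcomes and defines flare in the same phrase: "The incidence, intensity, time to peak and time to resolution of the flare reactions (defined as a 2-point increase from pre-injection pain". After the baseline reading, its pain readings are taken "immediately after the injection, five minutes after the injection, and once a day for a minimum of 7 days after the injection". Study Design & Methodology repeats both the rule and the schedule. Background & Significance gives the same threshold, citing reference 3, but a different schedule: "prior to the injection, during the injection and once a day for the following 7 days after the injection". The Statistical Analysis Plan lists the outcomes and the tests and adds no window. It also refers to the time to the flare, where the other sections have the time to its peak.

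Background & Significance describes the condition of interest as "a post-injection flare of increased pain that is attributed to crystal-induced synovitis". Risk & Benefit separately lists "typical risks associated with a trigger finger injection: pain at injection site, soreness". No section gives a rule for telling the two kinds of pain apart.

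**The concern.** A reading taken as the needle is withdrawn, or five minutes later, may reflect the injection itself rather than a crystal-induced reaction. Nothing in the rule excludes those readings, so any 2-point rise there meets the definition.

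The rule feeds incidence directly. It can also set the intensity, time to peak and time to resolution of whatever is counted. The Objectives section attaches weight to the result: "Findings indicating a statistically significant difference in the incidence and/or intensity of the flare reactions would be clinically significant", and such a finding is to be taken as support for changing practice. If analysts instead treat the window as unstated, two of them could follow the plan on the same data and report different incidences, and the choice could be made with results in view.

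**Working it through.** **1. What the text allows.** Take a patient at 3 before injection, 5 immediately afterwards, and 3 at five minutes and every day thereafter. Under the written rule this is a flare that peaks at once and resolves within minutes. Under a rule using only daily readings it is not a flare. The documents do not choose between the two.

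**2. The plan's own figure.** Target Population and the Statistical Analysis Plan state 30 patients for a 2-point difference with SD 2.5; Background & Significance makes this 30 per group and adds 80% power and 0.05 significance. Two-sided, n per group = 2 × (1.96 + 0.84)² × (2.5/2)² ≈ 24.5, so 25 (26 with the t-test). Thirty per group gives about 86% power by t-test, so the stated minimum is met. That calculation concerns a difference in mean VAS. The plan has none for flare incidence.

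**3. Incidence, same q in both arms.** Inputs:
- p1 = 33%, the upper incidence cited in Background & Significance.
- p2 = 5%, assumed.
- 40 per group, the top of the 30–40 in Target Population.
- q, the share with an in-clinic rise from injection pain, assumed and taken as independent of true flare.

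Counted rate = 1 − (1 − p)(1 − q), so the counted difference = (1 − q)(p1 − p2). Power is for the uncorrected chi-square test at two-sided 5%, by full binomial enumeration.

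| q | Counted rates | Difference (points) | Power |
|---|---|---|---|
| 0 | 33.0% vs 5.0% | 28.0 | 93.5% |
| 10% | 39.7% vs 14.5% | 25.2 | 73.5% |
| 30% | 53.1% vs 33.5% | 19.6 | 44.3% |

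Power passes below 80% at q of about 6.8%. With 33% versus 16.5% assumed instead, power goes from 40.5% to 28.9% and 19.3% at the same three values of q; the low starting point there is a sample-size matter, not this one.

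**4. Incidence, q differing between arms.** Let both true rates be 33%, with q = 10% in one arm and 20% in the other. Counted rates are 1 − 0.67 × 0.90 = 39.7% and 1 − 0.67 × 0.80 = 46.4%. The false difference is 6.7 points, and the test rejects in 9.9% of trials at 40 per group. With equal q and both true rates 33%, rejection stays between 4.8% and 5.6% for q from 0 to 50%.

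**5. The other flare outcomes.** The share of counted flares that are injection pain only is q(1 − p) / [1 − (1 − p)(1 − q)]. At q = 10% this is 0.067/0.397 = 17% in an arm with a true rate of 33%, and 0.095/0.145 = 66% in an arm with 5%. So even an equal q gives the two arms different mixtures when true incidence differs, and intensity, timing and resolution among counted flares are then compared across those mixtures.

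**The case against.** The strongest reply is that every size above rests on a q and a comparator rate that the documents do not give. Injection-site pain is listed as a risk without timing or severity, so its presence in the first five minutes is an inference. This stands: the omission is certain, the damage is not.

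Second, the trial is randomised and double-blinded with the same injected volume in both arms, and nothing in the documents suggests that q differs by product. This also stands. A reader might infer that the rule will produce false positives for incidence. The documents do not support that: with equal q the effect is dilution, and the unequal-q example only shows what could happen.

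Third, intensity may be meant as a whole-group comparison, since the objective also asks "if there are any differences in the peak level of pain and their duration" and the power calculation reads that way. Such a peak would not depend on counting flares, although an in-clinic reading could still supply it.

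Fourth, the literal rule is inclusive but prespecified, so it cannot be faulted as open-ended at the same time. That is fair. The two criticisms belong to two readings of the text, and each reading has its own cost.

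Two defences do not close the gap. The mechanism in Background & Significance hints at a narrower intent, but the operative rule does not carry it. Reference 3 is cited for the rule in that section only, and whether it sets a window cannot be checked from the documents.

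**Conclusion.** The point holds as something that should be fixed. The flare rule, the reading schedule and the Statistical Analysis Plan together leave in-clinic rises inside the definition, or leave the window to be chosen later.

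Under equal, independent q the incidence difference is multiplied by (1 − q). The power losses shown rest on an assumed 33% versus 5%, 40 per group and the stated q. A false incidence difference needs q to differ between products.

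A reader might also infer that mixed cases in time to resolution could by themselves drive the change-of-practice conclusion. They could not: that statement names incidence and intensity only, and with equal q the distortion in resolution arises only when true incidence already differs. Nor does the gap undermine the stated 30 per group, which concerns a mean VAS difference. The differing schedule and the two names for the timing outcome are side inconsistencies and do not add to the seriousness.

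**What to change.** Put one rule in Study Design, Background & Significance, Study Design & Methodology and the Statistical Analysis Plan, and fix it before unblinding:

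- **Flare:** a VAS at least 2 points above the pre-injection VAS on any once-daily reading in one fixed window common to all patients, for example days 1 to 7, day 1 being the day after injection. Injection-day readings do not define a flare.
- **Intensity, onset and time to peak:** taken from those same daily readings.
- **Resolution:** the first later daily reading less than 2 points above the pre-injection VAS, using the extended follow-up to two weeks where collected. Flares unresolved at the last reading are censored, so this outcome needs a method for censored times rather than the planned t-test.
- **In-clinic readings:** reported by arm as injection pain. An overall peak that includes them may stay as a separately labelled outcome, and incidence using all readings as a sensitivity analysis.
- **Consistency:** reconcile the schedule in Background & Significance with the other two sections, and use one name for the timing outcome.

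The cost is wording; the readings are already planned. The rule has limits. A flare that starts and ends before the first daily reading, or starts after the window, is missed, and soreness lasting into day 1 still counts. For example, if q = 30% and half of those rises persist to day 1, the effective q is 15%. With 33% versus 5%, the difference is then 0.85 × 28 = 23.8 points, between 19.6 as written and 28.0 with no mixing.

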**Study Duration –**

Enrollment: could take up to a year, depending on how long it takes to recruit enough patients.

Data Collection: 3-6 months after conclusion of patient enrollment

Analysis: 3-6 months after conclusion of data collection

## Section II: Design

### Background & Significance

Corticosteroid injections are effective non-surgical approach to treating trigger finger (stenosing tenosynovitis) with success rates reported as high as 92% after just one injection [1]. Among their side effects is a post-injection flare of increased pain that is attributed to crystal-induced synovitis [2]. Reports of these flares in the literature have been rare. Recent evidence their incidence can be as high as 33% [3]. We feel they are a more common clinical issue than traditionally reported and it would be beneficial to control and reduce their incidence if possible.

Two common corticosteroids used for trigger finger treatment are betamethasone and methylprednisolone [4][5]. Both injections are effective in treating trigger finger and the decision of which to use in treatment is currently a matter of the current practice and physician preference. There is no literature comparing the side effects, specifically flare reactions between these two treatments. Our goal through this randomized trial is to see whether there is a difference between

## OFFICE OF HUMAN RESEARCH PROTECTION

these two corticosteroids in inducing flare reactions and if there are any differences in the peak level of pain and their duration.

We will carry out a double-blinded randomized trial enrolling patients into one of the two treatment groups. The volume of the doses will be standardized to 1 cc of either methylprednisolone (40 mg) or betamethasone (6 mg). We will instruct patients who meet the inclusion criteria to complete a visual analog scale (VAS) of their pain (1-10) prior to the injection, during the injection and once a day for the following 7 days after the injection. We estimate that we need a minimum of 30 patients in each group to achieve a minimum of 80% power and 0.05 significance. The incidence, intensity, time to peak and time to resolution of the flare reactions (defined as a 2-point increase from pre-injection pain [3]) will be assessed and compared between the two groups. Findings indicating a statistically significant difference in the incidence and/or intensity of the flare reactions would be clinically significant and would be evidence supporting the switch of current practice to one corticosteroid over the other.

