**Study Design & Methodology**

The two standard of care corticosteroids used for trigger finger treatment are betamethasone and methylprednisolone. Both injections are effective in treating trigger finger and the decision of which to use in treatment is currently a matter of the current practice and physician preference. There is no literature comparing the side effects, specifically flare reactions between these two treatments. Our goal through this randomized trial is to see whether there is a difference between these two corticosteroids in inducing flare reactions and if there are any differences in the peak level of pain and its duration. We will carry out a double-blinded randomized trial enrolling patients into one of the two treatment groups. The volume of the doses of steroid to be given will be standardized to 1 cc of either methylprednisolone (40 mg) or betamethasone (6 mg). We will instruct patients who meet the inclusion criteria to complete a visual analog scale (VAS) of their pain (1-10) prior to the injection, immediately after the injection, five minutes after the injection, and once a day for a minimum of 7 days after the injection. The incidence, intensity, time to peak and time to resolution of the flare

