### Target Population & Recruitment Methods

We will recruit a minimum of 30-40 patients into each treatment group. Power analysis shows that at least 30 patients are needed to show a difference of 2-point difference between the two groups which corresponds to the minimal clinically important difference on the VAS scale assuming a standard deviation of 2.5 points. Accounting for the potential of patient data loss during follow-up surveys, we expect to need to consent and enroll 80-100 patients

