### Statistical Analysis Plan

Power analysis showed that a minimum of 30 patients are needed to show a difference of 2-point difference between the two groups which corresponds to the minimal clinically important difference on the VAS scale assuming a standard deviation of 2.5 points. We will compare the incidence, intensity, and time to flare reactions and time to resolution between the two groups using t-test and chi square tests as appropriate.

**Data Safety Monitoring** – Yes, there is a data safety monitoring plan in place for this study.

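### Time to resolution of a flare exists only in patients who flare, so the planned comparison is not randomised; define duration, intensity and flare for all patients from one set of readings

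*Combined protocol and SAP*

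**What the plan says.** Background & Significance and Study Design & Methodology name four outcomes: "The incidence, intensity, time to peak and time to resolution of the flare reactions (defined as a 2-point increase from pre-injection pain"). All four are worded as properties of flares. The Statistical Analysis Plan compares incidence, intensity, "and time to flare reactions and time to resolution between the two groups using t-test and chi square tests as appropriate". It names no analysis population, gives no value for a patient without a flare and has no rule for missed daily scores.

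Other text bears on who is analysed:

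- The aim is also put as finding out "if there are any differences in the peak level of pain and its duration", which could be measured in everyone.
- Target Population & Recruitment Methods says "at least 30 patients are needed to show a difference of 2-point difference between the two groups", with an SD of 2.5. Enrolment is raised to 80-100 only for lost data: "Accounting for the potential of patient data loss during follow-up surveys".
- Background & Significance states that a significant "difference in the incidence and/or intensity of the flare reactions would be clinically significant" and would support changing practice. Duration and time to peak are not in that sentence.

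The schedule of readings differs between sections. Background & Significance has a score during the injection and one on each of 7 days. Study Design & Methodology has scores "immediately after the injection, five minutes after the injection, and once a day for a minimum of 7 days after the injection", and lets follow-up run to two weeks where needed. Neither says which readings can make a flare.

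**The concern.** A patient who never flares has no time to resolution. At the rate the plan quotes ("Recent evidence their incidence can be as high as 33" per cent), about two thirds of patients drop out of that comparison, and which patients remain depends on the drug. If one drug prevents mild, short flares, those left on it are the longer ones, and it looks worse for having worked. Randomisation does not protect against this.

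Time to peak has the same problem as worded, although the day of highest pain could be defined for everyone. Intensity has it only if analysed in flarers. The choice matters there, because intensity alone may support a change of practice.

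The open window adds a second difficulty. If scores taken at or just after the injection count, pain from the needle itself could be classed as a flare.

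**Working it through.** **1. The plan's own sample size.** Inputs from the Statistical Analysis Plan and Background & Significance: difference 2, SD 2.5, alpha 0.05 (two-sided assumed), power at least 80%. Then n per group = 2 × (1.960 + 0.842)² × (2.5/2)² = 24.5, so 25, or 26 by the exact t-test. At 30, 40 and 50 per group the power is 86%, 94% and 98%. The stated 30 per group is sufficient for a comparison in all patients.

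**2. Duration.** The plan gives no flare durations, so these are assumed. On drug A, 22% have a 2-day flare and 11% a 5-day flare (33% in total). Flare days per patient are 0.22×2 + 0.11×5 = 0.99; the mean among flarers is 0.99/0.33 = 3.0 days. Drug B is better in each of four ways. Directions come from 40,000 simulated trials per cell, with 30 to 50 per group.

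| Drug B | Days per patient | Mean among flarers | Flare-only mean points the wrong way |
|---|---|---|---|
| prevents half of the short flares | 0.11×2 + 0.11×5 = 0.77 | 0.77/0.22 = 3.5 | 73-79% |
| prevents half of all flares | 0.11×2 + 0.055×5 = 0.495 | 0.495/0.165 = 3.0 | 47-48% |
| prevents half of the long flares | 0.22×2 + 0.055×5 = 0.715 | 0.715/0.275 = 2.6 | 20-24% |
| shortens every flare by one day | 0.22×1 + 0.11×4 = 0.66 | 0.66/0.33 = 2.0 | 2-6% |

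Days per patient are below 0.99 in every row. The all-patient mean points the right way in 69-96% of trials across the four. The flare-only mean is reversed on average in the first row and shows no benefit in the second, where drug B halves the number of flares.

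**3. Intensity, only if run in flarers.** Two assumed models span the range.

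- *The whole distribution shifts.* Peak change is normal with SD 2.5, and a flare is a change of at least 2. With a = (2 − mean)/2.5, the mean among flarers is mean + 2.5 × φ(a)/(1 − Φ(a)). A mean of 0.90 gives 33% flares with flarer mean 3.64. Two points lower (−1.10) gives 10.8% and 3.20; two points higher (2.90) gives 64.1% and 4.36. The true 2 points shrink to 3.64 − 3.20 = 0.44 or 4.36 − 3.64 = 0.72. Simulated power at 30/40/50 per group is 4/5/6% for the reduction and 18/24/30% for the increase. In the reduction case, 30 per group leaves about 30×0.33 = 9.9 against 30×0.108 = 3.2 flarers.
- *The full 2 points and SD 2.5 hold among flarers*, with 33% flaring in both arms. About 10, 13 and 16 flarers per arm give power of 39%, 50% and 59%.

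Both compare with 86-98% in step 1, which is for a 2-point difference in all patients.

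**4. The reverse case.** If drugs differ by 2 points among flarers only and 33% flare in each arm, the all-patient difference is 0.33×2 = 0.66. At SD 2.5 the all-patient power is 17%, 21% and 26%, against 39%, 50% and 59% in flarers. Here the all-patient test is the weaker one.

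**5. Lost data.** If 60 of 80-100 enrolled are analysed, the allowance is 1 − 60/80 = 25% to 1 − 60/100 = 40%. With 80 analysed it is 0-20%. The plan gives no rule for partly completed diaries.

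**The case against.** The strongest reply is that the decision does not rest on duration. Only incidence and intensity are said to support a change of practice, and incidence, tested in all patients, needs no value for non-flarers. This stands. A reader might infer that the flare-only duration test puts the trial's main conclusion at risk; the documents give duration no such role. It is still part of a stated objective.

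A reader might also infer that intensity will be tested in flarers, with about 4% power. The documents do not say so. The peak-pain objective and a sample size counted in patients, enlarged only for data loss, favour all patients. The 4% also belongs to one model; another gives 39% at 30 per group. What stands is that the text allows both readings.

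Nor do the figures show a sample-size error: 30 per group exceeds the 25 or 26 needed for 80% power.

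The 73-79% reversal comes from a pattern chosen to show the mechanism, and the other rows are milder. The flaw does not depend on how often reversal occurs, because the groups compared are not those that were randomised.

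Finally, the all-patient duration test is mostly zeros and close to an incidence test, and days 1 to 7 is one workable window among several. Both stand and are counted as costs below.

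**Conclusion.** The concern holds in a limited form. As worded, time to peak and time to resolution are to be tested in a subset formed after randomisation. For time to resolution this is unavoidable, and the result can point the wrong way: from 2-6% to 73-79% of trials, depending on which flares the better drug prevents or shortens. These rates rest on assumed flare durations, and only the 33% flare rate comes from the plan.

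For intensity the problem is an ambiguity. Nothing is lost if all patients are analysed and the drugs differ by 2 points overall. A flarer-only test would have 4-59% power across the models and sample sizes above. The flare window is undefined and the sections disagree on the readings, which also affects incidence. This should be settled before analysis, but it does not invalidate the trial.

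**What to change.** State in the Statistical Analysis Plan:

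1. **Intensity**: peak daily VAS on days 1 to 7 in all randomised patients with follow-up readings, by assigned group. The t-test is valid; ANCOVA on the pre-injection VAS is preferable. At 30 per group it would raise power from 86% to about 89-99% for assumed correlations of 0.3 to 0.7.
2. **Duration**: number of days 1 to 7 with VAS at least 2 points above pre-injection, 0 for patients without a flare. Report the mean difference with a bootstrap interval and a rank-sum test.
3. **Incidence**: chi-square in all patients, with a flare defined from the same daily readings. Report injection-time scores separately, and reconcile the schedules in Background & Significance and Study Design & Methodology.
4. **Descriptive only**: flare-only intensity, time to peak and time to resolution, including readings after day 7.
5. **Missing data and scale limit**: report missed days and complete dropouts by group, with a sensitivity analysis such as multiple imputation. Report how many patients start above 8 on the 1-10 scale and so cannot rise by 2 points.

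This needs no new patients, visits or data. The costs are statistical. If the drugs differ only in flare size, the intensity test loses power (17-26% against 39-59% in step 4). The duration test stays weak, at about 12-19% power when half of the short flares are prevented. Flare days after day 7 leave the tested duration, and two planned tests become descriptive.
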